5.1.3 Definitions

5.1.3.1 Baseline

For clinic visit based endpoints, baseline is defined as the last record or measure collected prior to the first dose of IMP.

For IVRS based endpoints, baseline will include all available data from the day of Visit 2 to Day 1 of the blinded phase.

5.1.3.2 Last Visit

Last visit for endpoints assessed at clinic visits is defined as the last scheduled visit (not including the end of taper or safety follow-up visits) at which patient's last evaluation is performed.

5.1.3.3 Last 12 Weeks (OLE Only)

The last 12 weeks (84 days) of the OLE for IVRS based endpoints is defined as all available data from 12 weeks prior to the earliest of the date of the patient completing the OLE, or the last call to IVRS.

5.1.3.4 Treatment Period

The treatment period of the double-blind phase is defined as Day 1 to Day 113.

5.1.3.5 Titration Period

The titration period of the double-blind phase is defined as Day 1 to Day 28.

5.1.3.6 Maintenance Period

The maintenance period of the double-blind phase is defined as Day 29 to Day 113.

5.1.3.7 TSC-associated Seizures

TSC-associated seizures are defined as focal motor seizures without impairment of consciousness or awareness, focal seizures with impairment of consciousness or awareness, focal seizures evolving to bilateral generalized convulsive seizures, and generalized seizures (tonic-clonic, tonic, clonic and atonic) that are countable.

5.1.3.8 Other Seizures

Other seizures are defined as absence, myoclonic, partial (focal) sensory seizures, and infantile or epileptic spasms.

5.1.3.9 Total Seizures

Total seizures are defined as the combination of TSC-associated seizures and other seizures.

5.1.3.10 Focal Seizures

Focal seizures are defined as Type 1, Type 2 or Type 3 as follows:

- Type 1: focal motor seizures without impairment of consciousness or awareness.
- Type 2: focal seizures with impairment of consciousness or awareness.
- Type 3: focal seizures evolving to bilateral convulsive seizures.

5.1.4 Interim Analysis

No formal interim analysis is to be conducted in this trial. However, interim reporting of the OLE may be required to support regulatory filings. This SAP contains details for the final reporting of the double-blind and OLE phases of the trial. For interim reporting of the OLE,

the rules described in the SAP will be followed. However, only a subset of outputs including OLE data may be required to support regulatory filings.

If interim reporting of the OLE is required, then only data available up to and including the date of the data cut will be included. The below section describes how data will be selected for the interim reporting.

5.1.4.1 Selection of Data and Handling of Partial Dates

For data that has an associated visit date or date of collection but does not have an associated start or end date, there is expected to be no partial date information. Therefore, data of this type that are collected after the date of data cut will not be included as part of the interim analysis. For non-medical history data that have an associated start date or end date, such as AEs or concomitant medications, the following rules will be followed in order to determine whether the records are included in the interim analysis.

Partial Start and/or End Dates

The following procedures will be followed in the event that a record has partial start or end dates:

Partial start date:

- If the start date is partial, then it will be assumed to have started at the earliest possible date based on the partial date provided, for the purposes of determining if the data should be included in the interim analysis only.

Partial end date:

- If the end date is partial, then it will be assumed to have ended at the latest possible date based on the partial date provided. However, if the patient withdrew from the trial, completed the trial or died prior to this imputed date, then the maximum of the last available visit date and the withdrawal/completion or death date will be used instead.

Once the dates have been suitably imputed, the processes for complete start or end dates, specified below, can then be followed to determine whether the record should be included in the data cut and how it should be adapted.

Complete Start or End Dates

The following procedures will be followed in the event that a record has complete start or end dates:

- If the start date falls on or before the date of data cut and the end date falls after the date of data cut, then the record will be included in the data cut but the end date will be set to missing and depending on the type of data, the following adjustments will be made:
 - For an AE record, the outcome will be set to "Continuing".
 - For a concomitant medication record, the record will be set to "Ongoing at the End of the Trial".
- If the start date falls after the date of data cut, then the record will not be included in the data cut.

5.2 Analysis Sets and Protocol Deviations

5.2.1 Safety Analysis Set

All randomized patients who received at least 1 dose of IMP will be included and analyzed according to the treatment received. Only patients for whom it has been confirmed that they did not take any IMP will be excluded from this safety analysis set.

5.2.2 Intention to Treat Analysis Set

All randomized patients who received at least one dose of IMP will be included and analyzed according to their randomized treatment arm.

The intention to treat (ITT) analysis set is the primary analysis set for all efficacy endpoints.

5.2.3 Per Protocol Analysis Set and Protocol Deviations

If there are a sufficient number of significant protocol deviations in the trial, a PP analysis set may also be presented.

All patients who complete the trial with no protocol deviations deemed to compromise the assessment of efficacy, will be included and analyzed according to the treatment arm they were randomized. The rules determining the PP analysis set will be fully defined prior to unblinding of the database.

A listing will be produced of protocol deviations for the clinical study report. These protocol deviations will be imported from the protocol deviations log. Protocol deviations will be classed as minor, important or major, where major deviations are classed as important protocol deviations leading to exclusion from the PP analysis set.

Protocol deviations were reviewed during BDRMs on 22nd and 25th March 2019. In addition to patients in the ITT analysis set who withdrew from the trial during the blinded treatment phase, a number of patients were deemed to have protocol deviations that should lead to exclusion from the PP analysis set. These patients, together with their deviations, are detailed in a separate document finalized prior to unblinding.

5.2.4 OLE Safety Analysis Set

The OLE safety analysis set will be defined as all patients who receive at least one dose of IMP during the OLE phase of the trial. Only patients for whom it has been confirmed that they did not take any OLE IMP will be excluded.

5.3 Listings

All data will be listed and ordered by site, treatment, patient number and, where appropriate, chronological order of assessment. Listings will be created for each of the subsequent sections of the SAP.

Visit date need not be included on all of the listings, but day numbers will be included, where appropriate.

Other derived variables (e.g. changes from baseline values) that are calculated for analysis purposes or to aid interpretation of the data will be added to the listings as appropriate.

5.4 Demographic Data and Patient Characteristics

5.4.1 Patient Disposition

Patient disposition, by site, by country and overall, will be summarized using standard summary statistics. The number screened, number of screen failures and number randomized will be included.

A screen failure disposition table will be presented, including number of patients screened, number failing screening, number randomized and the reasons for failing screening.

Patient disposition for the double-blind and OLE phases, including patients treated, completed the treatment and taper phases, discontinued (including reason for discontinuation) from the treatment and taper phases will be summarized by absolute counts (n) and percentages (%).

A further table split by site, and by country will be produced, showing number of patients randomized, withdrawn and completed the treatment phase at each site or in each country

5.4.2 Analysis Sets

Patients included in the safety, ITT, PP and OLE safety analysis sets, and patients excluded together with reasons for exclusion, will be summarized by absolute counts (n) and percentages (%).

5.4.3 Demographic Data and Baseline Characteristics

The following demographic data will be summarized by treatment arm and overall for the safety, ITT, PP and OLE safety analysis sets:

- Age (years);
- Age group (1–6 years, 7–11 years, 12–17 years and 18–65 years);
- Sex;
- Race;
- Country;
- Region (US, Rest of the World);
- Weight at baseline (kg);
- Height at baseline (cm);
- Body mass index at baseline (kg/m²).

Age will be calculated as:

$$(\text{Date of screening} - \text{date of birth}) \div 365.25.$$

The following baseline characteristics will be summarized by treatment arm and overall for the safety, ITT, PP and OLE safety analysis sets:

- Average number of TSC-associated seizures per 28 days during baseline.
- Average number of total seizures per 28 days during baseline.
- Number of patients with seizures during the baseline period, by seizure type.
- Number of AEDs a patient has used, prior to the trial and is no longer taking.

- Number of AEDs a patient is currently taking.
- Total number of prior and current AEDs.
- Number of patients taking clobazam (Yes, No, and if no, Prior).
- Number of patients taking valproic acid (Yes, No, and if no, Prior).
- Number of patients taking levetiracetam (Yes, No, and if no, Prior).
- Number of patients taking vigabatrin (Yes, No, and if no, Prior).

The number of prior AEDs no longer taking will be taken from the 'History of antiepileptic medications and therapies' CRF page. The number of AEDs a patient is currently taking is based on the 'Concomitant antiepileptic medications' CRF page. If a patient has a medication listed on both the 'History of antiepileptic medications and therapies' and 'Concomitant antiepileptic medications' CRF pages and the medication is considered concomitant (see Section 5.7.1) for the double-blind phase, then this will not be included in the number of prior AEDs no longer taking. AEDs starting after the last dose of IMP during the double-blind phase will not be counted.

Patients taking the same AED type, but where the AED were coded to different generic terms will be counted only once within the AED type. For example, valproate sodium, valproic acid, valproate semisodium and ergenyl chrono will all be counted as valproic acid and counted once under that term.

The number of patients taking clobazam is defined as the number of patients taking clobazam at any point during baseline period or treatment period. The same definition will apply for the number of patients taking each of the other AEDs. The number of patients taking other AED types will also be presented if the overall frequency of patients taking the AED is >25%.

Previous cannabis use will be included within the baseline characteristics listing.

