5.5.5 Subgroup Analyses

To assess the degree of effect heterogeneity, effect modifier analyses are proposed, on the ITT analysis set, for the primary efficacy endpoint and the key secondary efficacy endpoint of $\geq 50\%$ reduction in TSC-associated seizure frequency.

For the primary efficacy endpoint, the effect modifier analysis will be performed using the negative binomial regression analysis as described in Section 5.5.2. The model will be updated to include covariates for each level of the effect being tested (excluding a reference level), individually and with interactions with time, interactions with treatment arm and interactions with time and treatment. A separate model will be used for testing each effect. The treatment ratios (GWP42003-P vs. placebo), percent reduction and 95% confidence intervals will be presented for each level of the effect. In addition, the effect by time by treatment arm interaction p-value, testing the hypothesis that the effect level treatment ratios are homogeneous, will be presented.

For the key secondary efficacy endpoint of $\geq 50\%$ reduction in TSC-associated seizure frequency, patients with a $\geq 50\%$ reduction in seizure frequency will be modelled using logistic regression, including stratified age group and treatment arm as covariates. The model will also include covariates for each level of the effect being tested (excluding a reference level), individually and with interactions with treatment arm. A separate model will be used for testing each effect. The number and percent of responders, and odds ratios and 95% confidence intervals will be presented for each level of the effect. In addition, the effect by treatment arm interaction p-value, testing the hypothesis that the effect level odds ratios are homogeneous, will be presented.

The following effects will be tested:

- Age group (1-6 years, 7-11 years, 12-17 years and 18-65 years). Note: stratified age group will be removed as a covariate for this model.
- Sex (Male, Female).
- Region (US, Rest of the World).
- Clobazam use (Yes, No).
- Valproic acid use (Yes, No).
- . Levetiracetam use (Yes, No).
- Vigabatrin use (Yes, No).
- Baseline average TSC-associated seizures per 28 days (\leq observed Tertile 1, $>$ observed Tertile 1 to \leq observed Tertile 2, $>$ observed Tertile 2). The observed tertile values will be rounded to the nearest whole number.
- Number of concurrent AEDs (<3 , ≥ 3).
- Number of prior AEDs (<5 , ≥ 5).

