- Number of prior and concurrent AEDs (<8 , ≥ 8).

Effects of patients taking other AED types will also be tested if the overall frequency of patients taking the AED is $>25\%$.

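### The AED-use and AED-count effect modifiers apparently include AEDs started after randomization, so their interaction estimates can be biased

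*SAP*

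**What the plan says.** Under the title of baseline characteristics, SAP Section 5.4.3 counts as clobazam users all patients "taking clobazam at any point during baseline period or treatment period". It then extends the rule: "The same definition will apply for the number of patients taking each of the other AEDs". Section 5.1.3.4 fixes the window: "The treatment period of the double-blind phase is defined as Day 1 to Day 113".

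For the number of AEDs, Section 5.4.3 uses the concomitant AED page of the CRF and sets one limit: "AEDs starting after the last dose of IMP during the double-blind phase will not be counted". An AED begun during double-blind treatment therefore counts as current. Section 5.7.1 agrees, since a medication started on or after the first dose is concomitant.

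Section 5.5.5 states its purpose: "To assess the degree of effect heterogeneity, effect modifier analyses are proposed". The endpoints are the primary endpoint and the 50% responder endpoint, on the ITT set. The modifiers include yes/no use of clobazam, valproic acid, levetiracetam and vigabatrin; "Number of concurrent AEDs" split at 3; and prior plus concurrent AEDs split at 8. It adds that "Effects of patients taking other AED types will also be tested" when more than 25% of patients take them, the same threshold as in Section 5.4.3. It neither defines use nor refers back to Section 5.4.3. Addendum Section 2.3.2 plots results by clobazam use, also without a definition.

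**The concern.** An effect modifier should describe the patient before treatment. Here a patient who first takes clobazam late in the treatment period becomes a user for an outcome counted from Day 1. An AED may well be added because seizures are poorly controlled, and seizure control depends on arm. Patients who do badly would then move from the No group to the Yes group at different rates by arm. The comparison within each subgroup would no longer be protected by randomization.

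What is at stake is the reading of the interaction tests and subgroup estimates, and of the addendum plots that return to the clobazam split. A difference between users and non-users could come from the grouping rule rather than from the drug. Only starts matter for the named AEDs: a patient who stops one during treatment stays in the Yes group.

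**Working it through.** The SAP gives no figure for AED starts, so there is nothing to reproduce. Two illustrations show what the rule can do.

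**Inputs from SAP Section 3.2:** 70 patients per arm, mean change -15% on placebo and -50% on active (a 35-point effect), SD 60%. **Assumptions, not in the SAP:** the share of users at baseline, who starts an AED, and how starters fare.

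**1. Hand calculation.** Assume 21 of 70 users at baseline in each arm, baseline users at their arm's mean m, k late starters averaging +50%, and the arm mean held at m.

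- Yes mean = (21m + 50k) / (21 + k)
- No mean = (70m - 21m - 50k) / (49 - k)

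| Arm | k | Yes | No | Gap (Yes - No) |
|---|---|---|---|---|
| Placebo (m = -15) | 2 | (-315 + 100)/23 = -9.3 | (-735 - 100)/47 = -17.8 | 8.4 |
| Placebo | 3 | (-315 + 150)/24 = -6.9 | (-735 - 150)/46 = -19.2 | 12.4 |
| Active (m = -50) | 1 | (-1050 + 50)/22 = -45.5 | (-2450 - 50)/48 = -52.1 | 6.6 |
| Active | 2 | (-1050 + 100)/23 = -41.3 | (-2450 - 100)/47 = -54.3 | 13.0 |

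The false interaction is the placebo gap minus the active gap (differences taken before rounding):

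- 2 placebo and 1 active starter: 1.8 points, larger apparent effect in Yes.
- 3 placebo and 1 active: 5.7 points, same direction.
- 3 placebo and 2 active: -0.6 points, direction reversed.

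An active starter shifts its arm's gap more than a placebo starter does, because +50% lies further from -50% than from -15%.

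**2. Simulation, no true effect modification.** Change is normal with the means and SD above, 70 per arm. A share p are users at baseline, independent of outcome. Among non-users who worsen by more than 25%, a share q start the drug. The expected start rate is (1 - p) × q × P(change > 25). For p = 0.2 and q = 0.1 on placebo, P(Z > 40/60) is about 0.25, so the rate is 0.8 × 0.1 × 0.25 = 2%. There were 6,000 runs per case. The interaction is the effect in Yes minus the effect in No, so a negative value means a larger apparent benefit in Yes.

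| p | q | Starts, placebo / active | Interaction, any-use rule | Rejection, any-use rule |
|---|---|---|---|---|
| 0.2 | 0.10 | 2.0% / 0.9% | -3.4 | 6.6% |
| 0.2 | 0.25 | 5.0% / 2.1% | -7.2 | 7.9% |
| 0.2 | 0.50 | 10.0% / 4.2% | -12.2 | 10.8% |
| 0.3 | 0.10 | 1.8% / 0.7% | -2.1 | 6.1% |
| 0.3 | 0.25 | 4.4% / 1.9% | -5.4 | 6.3% |
| 0.3 | 0.50 | 8.8% / 3.7% | -10.6 | 9.5% |
| 0.4 | 0.10 | 1.5% / 0.6% | -1.7 | 5.2% |
| 0.4 | 0.25 | 3.8% / 1.6% | -4.5 | 5.8% |
| 0.4 | 0.50 | 7.5% / 3.2% | -9.3 | 8.0% |

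With q = 0, or with groups fixed by baseline use, the mean interaction is 0.3 to 0.5 points, which is simulation noise, and the test rejects in 5.3 to 5.5% of runs.

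Both illustrations use percentage change. The planned models are negative binomial for counts and logistic for responders, so the sizes are indicative only.

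**The case against.** The strongest reply is that nothing here shows bias. If no patient starts one of these AEDs during the 16 weeks, the any-use and baseline groupings differ only for AEDs stopped during baseline, and that cannot depend on arm. The protocol may restrict AED changes, and the SAP's PK section mentions disallowed concomitant medication without saying what it covers. This stands: the SAP supports that the estimates can be biased, not that they are.

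A reader might also infer from the placebo arm alone a false gap of 8 to 12 points that always favours users. That does not hold. It assumes no starters on active treatment, and a gap within placebo is not an interaction. Once active starters are allowed, the net figure shrinks and can change sign.

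The link from Section 5.4.3 to Section 5.5.5 is an inference, since there is no cross-reference. It is a strong one: the SAP offers no other definition of use, and the 25% threshold is repeated.

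Two further points stand. The effect-modifier analyses lie outside the Table 3 hierarchy, and the addendum plots are post hoc and descriptive. Also, a reader might want the liver-enzyme table in Section 5.6.3.1 regrouped by Day 1 use. That is not warranted, because exposure to valproic acid or clobazam during treatment is a defensible grouping for a safety summary.

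**Conclusion.** The point holds in a limited form. As written, the AED-use and AED-count modifiers of Section 5.5.5 apparently take in AEDs started after randomization, within the outcome window. Membership can therefore depend on arm and response. Whether the interaction estimates are in fact biased, by how much and in which direction cannot be told from the SAP, because it gives no start rate.

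Under the simulated assumptions the false interaction runs from none, with no starts, to about 12 points on a 35-point effect when about 10% of placebo and 4% of active patients start the drug. Rejection is then 8 to 11% across the assumed shares of baseline users, against about 5.5% with baseline grouping. The hand calculation shows that other patterns of starts can nearly cancel or reverse the direction.

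The weight is minor to moderate: no primary or key secondary test is affected.

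**What to change.** State in Section 5.5.5, and apply to the clobazam plots in addendum Section 2.3.2, that three things are defined by what the patient was taking before the first dose on Day 1:

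- use of each AED;
- the number of concurrent AEDs;
- the number of prior and concurrent AEDs.

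Add a rule for partial or missing AED dates. Section 5.7.1 treats unclear dates as concomitant, which does not settle whether the drug was in use before the first dose. Report AEDs started later as concomitant medication, and keep the any-use grouping at most as a sensitivity analysis. The liver-enzyme subgroup table may keep on-treatment exposure if it says so.

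The cost is a sentence or two and the date rule. AED start and stop days are already derived for the listings under Section 5.7.1, so no new data are needed. This is a free improvement.

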5.4.4 Epilepsy History

5.4.4.1 Genetic Testing History

Genetic testing history data will be listed only.

5.4.4.2 History of Seizures no Longer Occurring and History of Current Seizures

Data will be summarized by treatment arm and overall for the safety analysis set only, separately, for history of seizures no longer occurring and history of current seizures.

The following will be summarized by each seizure type:

- Number of patients with the seizure type.
- Age at onset (years).
- Age of last occurrence (years). For history of seizures no longer occurring only.
- Seizure duration (<2 minutes, 2–10 minutes, >10 minutes, Unknown). For history of current seizures only.

Seizure frequency data will be listed only.

For patients with more than one record for a particular seizure type, the earliest onset, most recent age of last occurrence and longest duration will be used for the summary table.

5.4.4.3 Neuroimaging History

Neuroimaging history data will be listed only.

5.4.5 Medical and Surgical History and Current Medical Conditions

All conditions and diagnoses on the 'non-epilepsy medical history' CRF page will be coded using Version 19.1 of the Medical Dictionary for Regulatory Activities (MedDRA v19.1).

The number of patients with relevant or significant non-epilepsy medical or surgical history and medical history by system organ class, and preferred term, will be summarized by absolute counts (n) and percentages (%). Percentages will be calculated based on the number of patients in the specific treatment arm. Two tables will be produced, one including any events classified as resolved at screening, and the other including all current conditions.

